Human Subjects Research Proposal

I. Study Title :

Effects of Combined Upper Extremity Exercise and Pneumatic Compression Therapy on Breast Cancer–Related Upper Extremity Lymphedema: A Single-Group Pretest–Posttest Follow-Up Study

II. Principal Investigator :

[name]

III. Co-Investigators :

[name], [name]

IV. Background :

Breast cancer–related lymphedema (BCRL) is a common long-term complication following breast cancer treatment. It is characterized by upper limb swelling, heaviness, pain, and restricted shoulder range of motion, which may significantly impair daily functioning and quality of life.

Previous studies have demonstrated that regular and moderate upper extremity exercise does not exacerbate lymphedema; instead, it may improve shoulder mobility and muscle strength and contribute to edema control (McKenzie & Kalda, 2003). In addition, pneumatic compression therapy and manual lymphatic drainage have been shown to reduce limb swelling and improve patient comfort (Moattari et al., 2013; Huang et al., 2013). Systematic reviews further indicate that exercise-based interventions have positive effects on upper limb function and quality of life in breast cancer survivors (Chan et al., 2010).

Therefore, combining upper extremity exercise with pneumatic compression therapy may represent a promising integrative rehabilitation strategy to improve lymphedema and associated functional impairments following breast cancer surgery.

V. Study Objectives :

This study aims to investigate the effects of combined upper extremity exercise and pneumatic compression device (PCD) therapy in patients with BCRL:

A. To evaluate the effects of 12 sessions of combined upper extremity exercise and mechanical intermittent pneumatic compression therapy on upper limb lymphedema.

B. To compare changes across three time points—baseline (T0), immediately after the 12th session (T1), and one-week follow-up (T2)—in:

1. Limb circumference measurements
2. Shoulder range of motion (ROM)

3. Disabilities of the Arm, Shoulder and Hand (DASH) scores
 4. Functional Assessment of Cancer Therapy–Breast (FACT-B) scores
- C. To assess short-term maintenance effects (T2), safety, and patient acceptability.

VI. Methods :

A. Eligibility Criteria and Sample Size

1. Sample Size:

20 participants will be recruited from this institution; no additional centers will participate.

2. Inclusion Criteria :

- (1) Female breast cancer patients aged 20–70 years
- (2) Unilateral breast cancer surgery with clinically diagnosed Stage I or II lymphedema (≥ 2 cm and < 8 cm inter-limb difference at least one measurement site)
- (3) Completion of adjuvant chemotherapy and/or radiotherapy at least 3 months prior
- (4) Ability to complete 12 treatment sessions and all assessments and provide written informed consent

3. Exclusion Criteria :

- (1) Evidence of breast cancer recurrence or metastasis
- (2) Severe upper limb infection (e.g., cellulitis)
- (3) Uncontrolled heart failure, deep vein thrombosis (DVT), or severe peripheral vascular disease
- (4) Stage III lymphedema, bilateral lymphedema, or use of medications affecting upper limb glandular function
- (5) Other upper limb musculoskeletal disorders, joint deformities, or prior upper limb surgery
- (6) Pregnancy or other contraindications

4. Recruitment :

Participants will be recruited from the outpatient Rehabilitation Department of Far Eastern Memorial Hospital. Recruitment announcements will be posted in the electrotherapy room. Eligible patients diagnosed with BCRL will be screened according to inclusion and exclusion criteria. A total of 20 participants will be enrolled.

B. Study Design :

This is a single-group prospective interventional study.

Study Procedures:

1. Screening and eligibility confirmation
2. Informed consent obtained in a private meeting room
3. Collection of baseline demographic and medical data
4. Study location: Rehabilitation Department electrotherapy room

Baseline Assessment (T0)

1. Primary Outcome: Limb Circumference Measurement

Measured using a standard flexible tape at predefined anatomical landmarks:

- Elbow joint
- 5, 10, 15 cm above elbow
- 5, 10, 15 cm below elbow
- Wrist

Standardization includes:

- Same assessor
- Same time of day (e.g., 9:00–12:00 AM)
- 10-minute seated rest prior to measurement
- Same body position

2. Shoulder Range of Motion (ROM)

Measured using a standard goniometer (active flexion, extension, abduction, adduction, internal and external rotation).

Two trials averaged; maximum pain-free range recorded.

3. DASH Questionnaire
4. FACT-B Questionnaire

Intervention Protocol

Total Sessions: 12

Frequency: 3 sessions per week

Duration: Approximately 4 weeks

Session Duration: ~50 minutes

1. Upper Extremity Exercise (30 minutes)
 - Warm-up (5 min): shoulder flexion, abduction, circular motion

- Active and resistance training (20 min): using elastic bands or 0.5 kg weights :
Seated rowing/Chest press/Lat pulldown/Single-arm row/Biceps curl/Triceps extension
Two sets of 10 repetitions (or up to 3 sets depending on tolerance)
 - Stretching (5 min): overhead stretch, lateral flexion, biceps/triceps stretch
2. Pneumatic Compression Therapy (20 minutes)
- Multi-chamber upper limb sleeve
- Sequential distal-to-proximal inflation
- Pressure range: 20–40 mmHg (adjusted according to tolerance and safety limits)
- Monitoring for pain, numbness, pallor, or circulatory compromise

Post-Intervention Assessment (T1)

Same measurements as baseline.

One-Week Follow-Up (T2)

Same measurements repeated.

Statistical Analysis

- Repeated Measures ANOVA
To assess overall differences across T0, T1, and T2.
Post hoc analysis will be conducted if significant.
- Paired t-test
To compare T0 vs. T1 and T0 vs. T2.

All tests will be two-tailed with significance set at $\alpha = 0.05$.

VII. Data Management

All data will be coded and de-identified.

Paper documents will be stored in locked cabinets.

Electronic data will be password-protected.

Data will be retained for five years and destroyed thereafter.

VIII. Participant Protection

Minor muscle soreness may occur.

If discomfort occurs three times, participation will be discontinued.

Participants may withdraw at any time without affecting clinical care.

Participants who complete the study will receive NT\$500 transportation reimbursement.

IX. Expected Outcomes

Significant improvements are anticipated in limb circumference, ROM, DASH, and FACT-B at T1, with partial maintenance at T2.

If confirmed, the findings may support a 12-session treatment protocol and inform future RCTs or cost-effectiveness studies.

X. Ownership of Results

Research results will belong to Far Eastern Memorial Hospital.

Findings may be published in academic journals or conferences.

No identifiable personal data will be disclosed.

XI. Conflict of Interest This study is investigator-initiated.

All investigators declare no conflicts of interest.

Any potential conflicts will be reported to the IRB.

XII. Reference

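### The primary outcome is eight circumference sites with no named summary variable or primary time point, and every test is at 0.05; tested site by site, the false-positive risk would be well above 5%

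*Protocol*

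**What the plan says.** - **Objectives (protocol section V.B).** Changes over T0, T1 and T2 are to be compared in four measures. The first is given in the plural, "Limb circumference measurements". No visit is singled out.
- **Baseline Assessment (section VI.B, item 1).** The heading is "Primary Outcome: Limb Circumference Measurement". The landmarks are the elbow joint, "5, 10, 15 cm above elbow", "5, 10, 15 cm below elbow" and the wrist: 1 + 3 + 3 + 1 = 8 sites. No sum, mean, volume, worst site or between-arm difference is defined as the analysis variable.
- **Statistical Analysis (section VI.B).** The ANOVA is there "To assess overall differences across T0, T1, and T2", with the line "Post hoc analysis will be conducted if significant". The next item is the paired t-test, "To compare T0 vs. T1 and T0 vs. T2", with no condition attached. The section closes with "All tests will be two-tailed with significance set at" 0.05. It mentions no order of testing and no adjustment.
- **Sample size (section VI.A).** 20 participants in one group.

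**The concern.** A primary outcome should tell the reader which one result decides the question. Here eight readings, three visits and two kinds of test all fall under the one label, each at 0.05. The plan leaves room to present a favourable p-value at any site and at either later visit as the primary result.

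The paired t-tests also overlap with the post hoc step: T0–T1 and T0–T2 are two of the three pairwise comparisons among three visits. If they are run whatever the ANOVA shows, making post hoc analysis conditional on the ANOVA does not limit the error for those two comparisons.

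Section IX says that confirmed improvements may support a 12-session treatment protocol and inform later randomised trials. In 20 patients without a control group, what counts as confirmation should be settled before the data are seen.

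**Working it through.** **Inputs from the protocol:** n = 20, 8 sites, 3 visits, two-sided 0.05 per test, one ANOVA and two paired t-tests.

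**Inputs assumed, because the protocol gives none:** an equal correlation between sites, varied from 0.3 to 0.9, and the correlation between visits. Two visit patterns were used: T0–T1 0.8, T0–T2 0.8, T1–T2 0.9 (pattern A); and all pairs of visits equal (pattern B).

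**The plan's own figure.** The 0.05 is a per-test design input. One variable with one contrast gives 1 − 0.95 = 0.05. The protocol states no familywise rate, so there is no other figure to reproduce.

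**Number of tests if every site is tested.** 8 × (1 ANOVA + 2 t-tests) = 24.

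**Reference values if tests were independent.**
- 8 tests: 1 − 0.95^8 = 33.7%.
- 24 tests: 1 − 0.95^24 = 70.8%.

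The second value overstates the risk, because the three tests at one site use the same data and the sites are correlated. Simulation is needed.

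**Simulation.** Null trials with normal data were generated, 20,000 per setting. Each site had an ANOVA F test (2 and 38 degrees of freedom) and two paired t-tests (19 degrees of freedom). The Monte Carlo standard error near 40% is √(0.4 × 0.6 / 20,000), about 0.35 percentage points.

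Chance of at least one false positive over the eight sites:

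| Between-site correlation | All three tests, A | All three tests, B | t-tests only after significant ANOVA, A | t-tests only after significant ANOVA, B |
|---|---|---|---|---|
| 0.3 | 46% | 52–54% | 32% | 26% |
| 0.5 | 40% | 45% | 27% | 22% |
| 0.7 | 31% | 35% | 20% | 17% |
| 0.9 | 20% | 23% | 13% | 11% |

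The 52–54% entry is the spread between separate runs, one of them with 8,000 replicates.

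**Outer limits under pattern B, all three tests.** Independent sites give 57%, and a between-site correlation of 0.99 gives 14%.

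**Narrower readings.**
- Eight sites, T0–T1 t-test only: about 12–30% for correlations 0.9–0.3.
- One summary variable, ANOVA and both t-tests ungated: about 8% (A) to 10% (B).
- One summary variable, t-tests only after a significant ANOVA: roughly 5%.
- One summary variable, one named contrast: 5%.

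**The case against.** **Site-by-site testing is not stated.** The protocol names one outcome and lists where it is measured; a sum, mean or volume would fit the text. A reader might infer that the plan prescribes 24 tests. It does not. This objection stands, so the site-level figures must be conditional.

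**The paired t-tests may be the post hoc comparisons.** They follow directly after the line on post hoc analysis. On that reading, one summary variable would have close to nominal error. This also stands as a possible reading, but the text does not settle it, and eight sites would still give 11–32%.

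**A SAP could supply the variable and the adjustment.** None was available for this review. Post hoc methods and adjustment procedures are commonly left to a SAP, so their absence alone is no fault. Which variable and which visit are primary is protocol content, however, and the 0.05 for all tests is fixed in the protocol itself.

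**Dilution and precision.** A reader might infer from the entry criterion, which requires a between-arm difference at one site or more, that many arms have nothing to reduce at other sites, or that pooling the sites must gain precision. The criterion is a minimum, and the protocol gives no data on how swelling is distributed. If swelling were local, a sum over all sites could dilute it too. Neither argument is relied on here.

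**Conclusion.** The point holds in conditional form. The primary outcome is not tied to one variable or one time point, and all tests are set at two-sided 0.05.

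If all eight sites are tested with all three tests, the false-positive chance is about 20–46% for between-site correlations of 0.9–0.3 under visit correlations 0.8/0.8/0.9, and about 23–54% with equal visit correlations. It is about 11–32% if the t-tests count only after a significant ANOVA. A single variable with all three tests ungated still gives about 8–10%.

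These ranges depend on assumed correlations and normal data. They should not be read as this trial's known error rate, and the protocol does not claim a familywise 5%. Two readings keep the error at or near 5%: one variable with one named contrast, or one variable with t-tests run only after a significant ANOVA. The text commits to neither.

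Severity: should be fixed. This is a small single-group study meant to inform later work, and the repair is simple.

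**What to change.** In the primary outcome item and the Statistical Analysis text of section VI.B:

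1. Name one primary circumference variable computed from readings already taken, for example the sum over the eight sites of the affected arm. The affected-minus-unaffected sum is an alternative if both arms are taped at every visit, which the protocol should then state.
2. Name one primary contrast from baseline and test it once at two-sided 0.05. Section IX expects the main improvement at T1, so T0 against T1 would be consistent with it.
3. Test the other time point only if the first test succeeds.
4. Make the ANOVA and the individual sites secondary.
5. Report ROM, DASH and FACT-B as secondary, either with adjustment or as estimates with 95% confidence intervals.

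**Cost.** With the affected-arm sum, this is a wording change, assuming that the affected arm is the one taped. The between-arm version may need extra measurements: the protocol refers to a between-arm difference only for eligibility and does not say that the unaffected arm is measured at T0, T1 and T2. The downside is that an isolated p-value at one site can no longer be claimed as primary success.

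### Tape tension is not standardized for the primary outcome; a constant-tension tape would be a cheap, optional safeguard in a study without a control arm

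*Protocol*

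**What the plan says.** Protocol section VI.B, Baseline Assessment (T0), names the "Primary Outcome: Limb Circumference Measurement" and gives the instrument: "Measured using a standard flexible tape at predefined anatomical landmarks". There are eight sites: the elbow, three levels above it, three below it, and the wrist.

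The standardization list that follows has four entries:
- "Same assessor"
- a fixed time-of-day window
- "10-minute seated rest prior to measurement"
- "Same body position"

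No tape tension, defined pull or gauge tape is mentioned there or elsewhere in the protocol. No repeat reading is stated for circumference. The rule "Two trials averaged; maximum pain-free range recorded" belongs to shoulder range of motion.

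T1 and T2 repeat the baseline measurements. The study has one group of 20, and no masking of the assessor is stated. The Statistical Analysis section plans a repeated measures ANOVA over the three time points and paired t-tests of T0 vs T1 and T0 vs T2, two-tailed at 0.05. Section IX says: "Significant improvements are anticipated in limb circumference, ROM, DASH, and FACT-B at T1, with partial maintenance at T2".

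**The concern.** Swollen soft tissue is compressible, so a firmer pull on a plain tape gives a smaller reading. With such a tape the pull is set by hand at each site and visit. The four listed items control who measures and the patient's physiological state, but not the pull.

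Two consequences follow, of different weight:
- **Random variation in pull.** This widens the SD of the change and costs precision. It does not raise the false-positive rate.
- **A shift linked to the visit.** If the same assessor, probably aware of the visit and expecting improvement, pulled slightly harder after treatment, the shift would enter the T0–T1 or T0–T2 change as apparent benefit. It could touch all eight sites together, so agreement between sites would not be independent support. In a randomized trial a shift common to both arms would tend to cancel. Here there is no second arm.

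Recording technique cannot be repaired in the analysis once readings are taken, so this is a matter for the protocol.

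**Working it through.** The protocol states no effect size, SD or power, so there is no figure of its own to reproduce. The calculation only shows how large a tension shift would have to be to matter.

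**Inputs from the protocol:** n = 20; paired t-test; two-sided α = 0.05.

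**Inputs assumed, because the protocol does not give them:** site girth 28 cm (also 16 cm for a small site); shift of 0.5%, 1% or 1.5% of girth; SD of change 0.5, 1.0, 1.5 or 2.0 cm; no true change; all 20 patients complete; affected-arm circumference analysed.

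**Step 1: the smallest mean change that reaches significance.** With 19 degrees of freedom the critical t is 2.093. The threshold is 2.093 / √20 = 0.468 SD of the change, which is 0.23, 0.47, 0.70 or 0.94 cm for the four SDs.

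**Step 2: shifts in centimetres.**
- 28 cm site: 0.14, 0.28 and 0.42 cm.
- 16 cm site: 0.08, 0.16 and 0.24 cm.

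**Step 3: probability of a significant result with no true change.** Under a constant shift b the t statistic is noncentral with noncentrality (b / SD) × √20. The probability is that of |t| > 2.093. For example, with b = 0.28 cm and SD = 1.0 cm, noncentrality is 0.28 × 4.472 = 1.252 and the probability is 0.221.

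| Site and SD of change | 0.5% shift | 1% shift | 1.5% shift |
|---|---|---|---|
| 28 cm, SD 0.5 cm | 22.1% | 66.1% | 94.5% |
| 28 cm, SD 1.0 cm | 9.1% | 22.1% | 43.0% |
| 28 cm, SD 1.5 cm | 6.8% | 12.5% | 22.1% |
| 28 cm, SD 2.0 cm | 6.0% | 9.1% | 14.5% |
| 16 cm, SD 1.0 cm | 6.3% | 10.4% | 17.5% |

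The nominal rate is 5%. The direction is the same in every row, but the size depends heavily on the SD and on the girth of the site. No single row should be read as the expected error rate.

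**The case against.** **The list need not be exhaustive.** It is introduced as what standardization includes, so a separate working procedure might cover tension. That is fair, but the protocol points to none.

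**One assessor already removes the main source of variation.** Differences between hands are dealt with. This stands, and it narrows the point to drift or expectation within one assessor.

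**The bias is hypothetical.** A reader might infer that a firmer pull at T1 will occur and will be read as reduced swelling. The documents do not support that. They show only that pull is not fixed, that no masking is stated and that improvement is expected. That the assessor knows the visit is a reasonable inference, not a stated fact.

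**The effect need not enter in full.** A reader might also infer that any shift passes wholly into the effect estimate. That holds only if affected-arm circumference is analysed. Eligibility is defined by inter-limb difference, and the protocol does not say which form the outcome takes. If the difference is analysed and both arms are pulled alike, part of the shift cancels. The planned T0–T2 comparison and the ANOVA are further estimates, though they rest on the same tape readings.

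**A gauge tape does not cure expectation.** Landmark placement and reading remain open to it. This also stands. A written definition of pull would be a lighter step, but harder to enforce.

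**Conclusion.** The point holds as a cheap improvement of optional weight. It is not an error in the plan. The primary outcome is read with a plain tape whose tension is not standardized, in a design where a visit-linked shift would have no control arm to cancel it. A shift of a few millimetres could matter with 20 patients: under the assumed inputs the false-positive probability at a 28 cm site runs from 6% (0.5% shift, SD 2.0 cm) to about 95% (1.5% shift, SD 0.5 cm), and it is lower at a smaller site with the same SD. Those figures rest on assumed girth, shift and SD, on there being no true change, and on the shift being systematic. Whether any such shift would occur cannot be judged from the protocol.

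**What to change.** In section VI.B, replace the standard flexible tape with a constant-tension (spring-gauge) tape, read at the same gauge mark at every site and at T0, T1 and T2. Add fixed tape tension to the standardization list.

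The cost is one inexpensive tape, brief familiarization for the assessor, and a line or two of protocol text. The downside is that readings will not be interchangeable with earlier clinic values taken with a plain tape. The change controls tension only; it leaves any expectation effect in landmark placement or reading untouched.

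### The discomfort rule ends participation, not only treatment, and T1 is tied to the 12th session, so read literally a patient stopped early is lost from the planned comparisons

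*Protocol*

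**What the plan says.** Protocol, Section VIII (Participant Protection): "If discomfort occurs three times, participation will be discontinued". Voluntary withdrawal has its own sentence there: "Participants may withdraw at any time without affecting clinical care". The same section pays the NT$500 travel reimbursement only to patients who complete the study.

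Section V.B (Study Objectives) lists the time points after baseline as "immediately after the 12th session (T1), and one-week follow-up (T2"). In Section VI.B the matching procedure is headed "Post-Intervention Assessment (T1") and gives no session number. The treatment course is 12 sessions at three per week ("Duration: Approximately 4 weeks").

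The statistical analysis in VI.B is a repeated measures ANOVA ("To assess overall differences across T0, T1, and T2") with paired t-tests of T0 against T1 and T0 against T2. The planned sample is 20.

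**The concern.** The rule and the visit definition interact. If participation ends at the third episode of discomfort, and T1 exists only after session 12, a patient stopped earlier never reaches T1 and is out of the study before T2. She has a baseline value and nothing to compare it with.

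The patients affected are those who tolerate the programme poorly. They matter for the safety and acceptability aim in V.C, and for Section IX, which looks ahead to supporting a 12-session treatment protocol. If they also benefit less, a result from completers alone is too favourable for patients who start the programme. If they benefit equally, the cost is precision out of 20 patients.

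The loss is avoidable. The stop is imposed by the protocol and is listed apart from withdrawal, so a stopped patient has not withdrawn consent and could still be measured. How to analyse missing values can be left to a statistical analysis plan. Whether the measurements are taken cannot.

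**Working it through.** **Reading the text.** The protocol states no dropout allowance and no discomfort rate, so there is no figure of its own to reproduce. Taking VIII, V.B and VI.B together:

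- Third episode before session 12: T0 only. The patient enters neither the ANOVA nor either t-test.
- Third episode at session 12: T1 may be kept, T2 is lost. The patient enters at most the T0–T1 test.
- With at most one episode per session (an assumption; the protocol counts occurrences, not sessions), the first case covers sessions 3 to 11.

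**Illustrative size.** Inputs from the protocol: 12 sessions, 20 patients, stop at the third episode, two-sided 0.05. Assumed: per-session probability of discomfort p from 0.05 to 0.20, and at most one episode per session.

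With independent sessions, the fraction lost from T0–T1 is f = 1 − BinomCDF(2; 11, p). The fraction lost from T0–T2 and the ANOVA is 1 − BinomCDF(2; 12, p). For p = 0.20, f = 1 − (0.0859 + 0.2362 + 0.2953) = 0.3826, and 20 × 0.3826 = 7.65 patients. The clustered columns use a beta-binomial with an assumed intraclass correlation of 0.3.

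| p | T0–T1 lost of 20, independent | T0–T2 and ANOVA lost of 20, independent | T0–T1 lost of 20, clustered | T0–T2 and ANOVA lost of 20, clustered |
|---|---|---|---|---|
| 0.05 | 0.3 | 0.4 | 1.6 | 1.7 |
| 0.10 | 1.8 | 2.2 | 3.3 | 3.5 |
| 0.15 | 4.4 | 5.3 | 5.0 | 5.4 |
| 0.20 | 7.7 | 8.8 | 6.8 | 7.2 |

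**Precision.** The paired standardized effect detectable with 80% power (noncentral t) is 0.66 SD with 20 pairs, 0.70 with 18, 0.75 with 16 and 0.89 with 12.

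**Possible overstatement.** Set the completers' mean T0–T1 change to 1 and let stopped patients gain a fraction r of it. The ratio of the completer mean to the all-enrolled mean is 1 / (1 − f(1 − r)).

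- Equal gain (r = 1): the ratio is 1.00 whatever p is.
- Gain proportional to sessions received (r = mean stopping session / 12): given a stop by session 11, the mean stopping session is 8.8, 8.6, 8.3, 8.1 for the four values of p (independent) and 6.8, 6.6, 6.5, 6.3 (clustered). The ratios are 1.00, 1.03, 1.07, 1.14 and 1.04, 1.08, 1.13, 1.19. For p = 0.15, independent: r = 8.34/12 = 0.695, and 1 / (1 − 0.2212 × 0.305) = 1.07.
- No gain (r = 0), independent, p = 0.20: 1 / (1 − 0.3826) = 1.62. This is an illustrative scenario and not a bound, since stopped patients could worsen.

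**The case against.** **The text.** The point leans on one word in a one-line safety statement. The protocol nowhere forbids measuring a stopped patient, the authors may have meant treatment, and the VI.B heading for T1 could be read as an assessment whenever treatment ends. That softer reading is possible but nowhere stated. V.B is explicit about session 12, and T2 would still fall after participation has ended. What stands is that this is a literal reading; a claim that the protocol prohibits such measurements would go too far.

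**The size.** It rests wholly on assumptions. Weights are light, compression pressure is "adjusted according to tolerance and safety limits", extra sets depend on tolerance, and entry requires "Ability to complete 12 treatment sessions and all assessments". These features make repeated discomfort less likely by an unknown amount, though the entry criterion is judged beforehand and does not prevent a later stop. This stands as a limit on the magnitude.

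**The remedy.** Changing Section VIII alone would contradict V.B. A completer's T1 directly follows 20 minutes of compression, whereas a stopped patient's would not, and her T2 would come more than one week after her last session. Pooling both groups also moves objective A from the effect of 12 sessions to the effect of starting the programme. Stopped patients would need a separate trip, which the reimbursement wording does not cover. All of this stands, and the change below has to deal with it.

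**A stronger inference.** A reader might conclude that the trial will overstate benefit. The documents do not show that poor tolerators gain less, so neither the presence nor the direction of bias is established.

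**Conclusion.** The point holds as a literal reading of Section VIII with V.B: stopping before session 12 leaves only T0, and stopping at session 12 loses T2. The loss is selected by tolerance and cannot be repaired at analysis.

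Its size is unknown. Under the assumed rates it runs from negligible (0.3 of 20 at p = 0.05, independent sessions) to serious (7.7 of 20 at p = 0.20), and clustering raises the low end to 1.6. A reader might take the upper figures as a forecast; without a discomfort rate in the protocol they are not one.

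It should be fixed because the change is small and measurements not taken are gone for good. The threshold of three episodes for stopping sessions is not questioned.

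**What to change.** 1. Section VIII: *After a third episode of discomfort, treatment sessions will be stopped; the patient will still be assessed at the calendar time of T1 (about week 4) and T2 (one week later) unless she withdraws consent.*
2. Section V.B: define T1 as directly after session 12, or at about week 4 if sessions were stopped early.
3. Section VIII: extend the transportation reimbursement to stopped patients who attend these visits.
4. Analysis: report all assessed patients as the effect of starting the 12-session programme, with the 12-session completers alongside. Note that a stopped patient's T1 does not directly follow compression and that her T2 falls more than one week after her last session.

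Cost: a few sentences of wording, a separate trip for each stopped patient, the reimbursement for those who attend, and possibly a less favourable estimate. No visits are added beyond the 20 × 2 = 40 post-baseline assessments already planned. If every stopped patient returned, the expected number kept instead of lost would be 20 × (0.0152 + 0.0196) = 0.7 at p = 0.05 and 20 × (0.3826 + 0.4417) = 16.5 at p = 0.20, with independent sessions.

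### The travel reimbursement is stated only for completers while a third discomfort ends participation, which gives some motive to under-report discomfort and could tilt the safety and acceptability objective

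*Protocol*

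**What the plan says.** Section V, objective C, reads "To assess short-term maintenance effects (T2), safety, and patient acceptability".

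Section VIII (Participant Protection) holds four statements that bear on it:
- On expected effects: "Minor muscle soreness may occur".
- On stopping: "If discomfort occurs three times, participation will be discontinued". No type, severity or attribution is attached to the word discomfort.
- On withdrawal: "Participants may withdraw at any time without affecting clinical care".
- On payment: "Participants who complete the study will receive" NT$500, described as a transport reimbursement. Nothing is said about participants who withdraw or are discontinued.

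In section VI.B, the compression component carries the line "Monitoring for pain, numbness, pallor, or circulatory compromise", and the pressure is set within its range by what the patient tolerates. At T1 the plan is "Same measurements as baseline", that is, circumference, ROM, DASH and FACT-B. T2 repeats them.

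**The concern.** The payment and the stopping rule are each ordinary. The difficulty comes from reading them together. A participant stopped at her third discomfort does not complete, so she has no stated claim to the travel money. Mentioning a third episode therefore costs her the remaining sessions and the reimbursement for trips already made. The promise that withdrawal leaves clinical care unaffected does not cover this payment.

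Pain, numbness and soreness are known to staff mainly because the patient mentions them. If she has a reason not to, two things suffer. The record from which objective C would naturally be judged becomes milder than the experience behind it, and tolerance-based monitoring loses part of its input. With one group and 20 participants, no comparison arm would reveal the gap, and no later analysis can recover symptoms that were never reported.

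Expected muscle soreness is not separated from the discomfort that counts towards stopping. If ordinary soreness counts, the motive may arise often.

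**Working it through.** The Protocol gives no discomfort, completion or dropout figure, so there is nothing of its own to reproduce.

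**1. What a non-completer forgoes.** Inputs: NT$500 (section VIII), 12 sessions, T1 right after session 12, and T2 one week later. Assumptions: T1 falls on the day of session 12, and each visit has an equal share.
- T0 on the day of session 1: 12 + 1 = 13 visits, 500/13 = NT$38.5 per visit. After session 11, 11 visits have been made: 11 × 500/13 = NT$423.
- T0 as a separate visit: 12 + 1 + 1 = 14 visits, 500/14 = NT$35.7 per visit. After session 11, 12 visits have been made: 12 × 500/14 = NT$429.
- With at most one episode per session, the earliest stop is after session 3: 3 × 500/13 = NT$115, or 4 × 500/14 = NT$143.

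On the natural reading she receives NT$0 in each case.

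**2. What the stopping rule shows when everyone is counted.** Let p be the chance of a counted discomfort in a session, independent across sessions and at most one per session. Both p and this model are assumptions. P(discontinued) = P(X ≥ 3) with X ~ Binomial(12, p). The completer mean rate is E(X | X ≤ 2)/12.

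| p | P(discontinued) | Expected of 20 | Mean discomfort rate among completers |
|---|---|---|---|
| 0.05 | 0.020 | 0.4 | 4.6% |
| 0.10 | 0.111 | 2.2 | 7.8% |
| 0.20 | 0.442 | 8.8 | 11.5% |
| 0.30 | 0.747 | 14.9 | 13.4% |
| 0.50 | 0.981 | 19.6 | 15.2% |

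Counted over all 20, frequent discomfort is plainly visible. Described in completers only, it is capped: nobody can have more than 2 of 12 sessions with discomfort (16.7%), whatever the true rate.

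**3. What under-reporting could do.** If a fraction r of episodes is reported, replace p by p × r. Expected completers = 20 × P(X ≤ 2) with X ~ Binomial(12, p × r).

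| p | r = 1 | r = 0.75 | r = 0.50 | r = 0.25 |
|---|---|---|---|---|
| 0.20 | 11.2 | 14.7 | 17.8 | 19.6 |
| 0.30 | 5.1 | 9.4 | 14.7 | 18.9 |
| 0.50 | 0.4 | 2.3 | 7.8 | 16.4 |

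At p = 0.30 the same experience could appear as about 5 or about 19 completers of 20, depending on r. This shows how sensitive the completion count is to reporting. It does not estimate r, and nothing in the Protocol says that the payment would move r by any given amount.

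**The case against.** The case against has several sound parts.

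- **A reader might infer that objective C will look favourable whatever patients experience.** The documents do not support that. The stopping rule turns discomfort into early exits, and step 2 expects about 9 of 20 at p = 0.20 and about 15 of 20 at p = 0.30 when reporting is full and all enrolled are counted. A favourable tilt needs under-reporting or a description limited to completers.
- **A reader might infer that acceptability is judged by completion.** The Protocol never says so, nor that discontinued participants are left out of the safety description. Measures and denominators may be set in an SAP that is not at hand, so their absence is not a finding.
- **A reader might take inclusion criterion (4), "Ability to complete 12 treatment sessions and all assessments and provide written informed consent", as selection for tolerant patients.** It is a feasibility screen. It limits how far a completion rate carries over to other patients, but gives no ground for changing the criterion.
- **The rule speaks of discomfort occurring, not being reported.** Staff can see pallor and circulatory compromise for themselves. That stands, but pain, numbness and soreness still depend largely on the patient's word.
- **Forfeiture is inferred.** Section VIII does not say that only completers are paid, and the consent form, which may set other terms, is not at hand. Payment on completion remains the natural reading.
- **The sum is small.** At about NT$36 to NT$38 per visit the pull may be weak. This limits the importance of the point, but the incentive still runs the wrong way.

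**Conclusion.** The concern holds in a limited form. As worded, section VIII ties a travel reimbursement to completion and also makes a third discomfort end participation. Together these give some motive to under-report, worth at most a few hundred NT$ to a participant (about NT$423 to NT$429 after session 11). The likely direction is favourable to objective C and unhelpful to tolerance-based monitoring. The size is unknown: the tables above rest on assumed discomfort and reporting rates and an independence model, and show only what is possible.

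The conclusion rests on reading the payment clause as excluding non-completers. If the consent already pays them, the payment part falls away. The wording on soreness and discomfort would still need reconciling. The point does not show that the trial cannot assess safety or acceptability. It supports an inexpensive improvement made before enrolment, because payment and stopping terms belong to the protocol and consent and cannot be repaired in the analysis.

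**What to change.** - Pay the transport reimbursement per attended visit, up to the same NT$500, to every participant, including those who withdraw or are discontinued.
- State in the consent that reporting discomfort does not affect payment.
- Report safety and acceptability on all enrolled participants, and count discontinuations, with reasons, as outcomes. Record discomfort episodes by session so that those before a discontinuation are kept. If the SAP already provides this, a cross-reference is enough.
- Have the sponsor reconcile the expected muscle soreness with the discomfort that counts towards discontinuation, so that both passages use the term in the same way. No threshold is proposed here.

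Cost: a protocol and consent amendment, slightly more payment paperwork and possibly a few more early stops. Total payment stays within 20 × 500 = NT$10,000, the most the present wording already implies.
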